# 7. STATISTICAL/ANALYTIC ISSUES

# 7.1. HANDLING OF DROPOUTS OR MISSING DATA

Only the following missing data will be imputed and analyzed in tables summaries. Imputed data will not be presented in listing. All other missing data will not be imputed.

#### Severity of AE

If severity of AE is missing, 'Severe' AE will be imputed for analysis.

#### **Causality of AE**

If the relationship of AE to investigational product is missing, 'Related' will be imputed for analysis.

## 7.2. Interim Analyses and Data Monitoring

No interim analyses or data monitoring are planned for this study.

Document: \\SW20RND01\\VistaTempDir\Temp28232\\Shire\_0624\_209\_SAP\_v1 0.docx

Author: PPD Version Number: 1.0
Version Date: 21Jul2017

Template No: CS\_TP\_BS016 Revision 4 Reference: CS\_WI\_BS005

Effective Date: 01Apr2016

reproduction is strictly prohibited.

PROTOCOL: 0624-209 Page 28 of 35

> 1.0 21Jul2017

## 9. APPENDICES

# 9.1. APPENDIX I – LIST OF STATISTICAL OUTPUTS

#### 9.1.1. LIST OF PLANNED TABLES

Table 14.1.1.1 Subject Disposition (All Screened Subjects)

Table 14.1.2.1 Protocol Deviations (Intent-to-Treat Safety Analysis Set)

Table 14.1.4.1 Demographic and Baseline Characteristics (Intent-to-Treat Safety Analysis Set)

Table 14.1.4.3.1 Summary of HAE History (Intent-to-Treat Safety Analysis Set)

Table 14.1.4.3.2 Summary of Medical History (Intent-to-Treat Safety Analysis Set)

Table 14.1.4.4 Prior Medications and Therapy (Intent-to-Treat Safety Analysis Set)

Table 14.1.4.5 Concomitant Medications and Therapy (Intent-to-Treat Safety Analysis Set)

Table 14.2.1.1 Summary of Angioedema Attacks during Treatment Period (Full Analysis Set)

Table 14.2.1.2.1 Sensitivity Analysis Completed Schedules - Summary of Angioedema Attacks during Treatment Period (Full Analysis Set)

Table 14.2.1.2.2 Sensitivity Analysis Treatment Compliance - Summary of Angioedema Attacks during Treatment Period (Full Analysis Set)

Table 14.2.1.3 Analysis of Clinical Responder Rate – Achieving at least 50%, 70% or 90% Reduction Relative to Historical Data in NNA (Full Analysis Set)

Table 14.2.2.1.1 Summary of Breakthrough Angioedema Attacks Treated By CINRYZE (Full Analysis Set)

Table 14.2.2.1.2 Summary of Breakthrough Angioedema Attacks Treated By Non-CINRYZE C1-INH (Full Analysis Set)

Table 14.2.2.1.3 Summary of Other Breakthrough Angioedema Attacks Not Treated with C1-INH (Full Analysis Set)

Table 14.2.2.1.4 Summary and Change from Baseline on AE-QoL (Full Analysis Set)

Table 14.2.3.1 C1-INH Antigen, Functional C1-INH activity, Complement C4 and C1q (Intent-to-Treat Safety Analysis Set)

Table 14.2.3.2 Antibody Results (Intent-to-Treat Safety Analysis Set)

Table 14.3.1.1 Overall Treatment-emergent Adverse Events (TEAEs) (Intent-to-Treat Safety Analysis Set)

Table 14.3.1.2.1 Treatment-emergent Adverse Events by System Organ Class and Preferred Term (Intent-to-Treat Safety Analysis Set)

Document: \\SW20RND01\\VistaTempDir\Temp28232\\Shire\_0624\_209\_SAP\_v1 0.docx

Version Date: 21Jul2017

Version Number:

1.0

Template No: CS TP BS016 Revision 4 Reference: CS WI BS005

Effective Date: 01Apr2016

Author:

Table 14.3.1.2.2 Serious Treatment-emergent Adverse Events by System Organ Class and Preferred Term (Intent-to-Treat Safety Analysis Set)

Table 14.3.1.3.1 Treatment-emergent Adverse Events by Preferred Term (Intent-to-Treat Safety Analysis Set)

Table 14.3.1.3.2 Serious Treatment-emergent Adverse Events by Preferred Term (Intent-to-Treat Safety Analysis Set

Table 14.3.2.1 Treatment-emergent Adverse Events by Maximum Severity, System Organ Class and Preferred Term (Intent-to-Treat Safety Analysis Set)

Table 14.3.2.2 Treatment-emergent Adverse Events Considered Related to Investigational Product by System Organ Class and Preferred Term (Intent-to-Treat Safety Analysis Set)

Table 14.3.4.1 Quantitative Clinical Laboratory Results: Hematology (Intent-to-Treat Safety Analysis Set)

Table 14.3.4.2 Quantitative Clinical Laboratory Results: Clinical Chemistry (Intent-to-Treat Safety Analysis Set)

Table 14.3.4.3 Quantitative Clinical Laboratory Results: Coagulation (Intent-to-Treat Safety Analysis Set)

Table 14.3.4.4 Quantitative Clinical Laboratory Results: Urinalysis (Intent-to-Treat Safety Analysis Set)

Table 14.3.4.5 Shift from Baseline in Clinical Laboratory Results: Hematology (Intent-to-Treat Safety Analysis Set)

Table 14.3.4.6 Shift from Baseline in Clinical Laboratory Results: Clinical Chemistry (Intent-to-Treat Safety Analysis Set)

Table 14.3.4.7 Shift from Baseline in Clinical Laboratory Results: Coagulation (Intent-to-Treat Safety Analysis Set)

Table 14.3.4.8 Shift from Baseline in Clinical Laboratory Results: Urinalysis (Intent-to-Treat Safety Analysis Set)

Table 14.3.4.9 Subjects with Potentially Clinically Important (PCI) Laboratory Results (Intent-to-Treat Safety Analysis Set)

Table 14.3.5.1 Actual Values and Change from Baseline in Vital Signs (Intent-to-Treat Safety Analysis Set)

Table 14.3.5.2 Potentially Clinically Important Vital Signs Results (Intent-to-Treat Safety Analysis Set)

Table 14.3.6 Study Drug Exposure (Intent-to-Treat Safety Analysis Set)

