| 6 hours after start of infusion | X ^c | | | X ^c | A |
| 24 hours after start of infusion | X ^d | | | X ^d | |
| 48 hours after start of infusion | X ^d | | | X ^d | |
| 72 hours after start of infusion | X d, e | | | X ^d | |
| 96 hours after start of infusion | X d, f | | | X ^d | |

C1 INH=C1 inhibitor; PD=pharmacodynamics; PK=pharmacokinetics

- a: C1q concentration will also be assessed from the baseline sample (pre-infusion at Dosing Visit 1).
- b: Collect within ± 5 min of the specified time.
- c: Collect within \pm 15 min of the specified time.
- d: Collect within ± 2 h of the specified time.
- e: If Dose 2 is scheduled to be administered 3 days after Dose 1, the 72-hour sample should be collected pre-infusion and the 96-hour sample should be omitted.
- f: If Dose 2 is scheduled to be administered 4 days after Dose 1, the 96-hour sample should be collected pre-infusion.
- g: If a subject prematurely discontinues on a day when PK/PD assessments are scheduled every effort should be made to collect the PK/PD sample(s) as indicated. If a subject discontinues on a day when PK/PD assessments are not scheduled, a single PK/PD blood sample should be collected with sampling time recorded in the CRF.

NOTE: If a subject presents to the site with a breakthrough angioedema attack, every effort should be made to obtain a PK blood sample before treatment. In addition, if the subject receives CINRYZE for treatment of the attack, every effort should be made to obtain a 1-hour post-treatment sample; if a second dose of CINRYZE is administered, an additional 1-hour post-treatment sample should be obtained if possible. These samples will be collected as an unscheduled visit and analyzed for C1 INH antigen (protein volume) and functional C1 INH activity (potency).

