6.12.1 Treatment of Breakthrough Angioedema Attacks

A breakthrough attack is defined as an angioedema attack that occurs during long-term prevention therapy with CINRYZE. If a subject receives CINRYZE for treatment of a breakthrough angioedema attack, they should continue their protocol-defined treatment schedule without alteration regardless of when the supplemental dose is administered.

If a breakthrough angioedema attack occurs during the 12-week treatment period through 1-week post-treatment, a supplemental dose of CINRYZE may be administered by IV infusion for treatment of the attack either by the Investigator (or qualified delegate) or subject (or caregiver) if trained and deemed independent to self-administer (1000 U for subjects ≥6 years of age or 500 U for subjects 2-5 years of age). If the subject does not adequately respond to the initial dose within 1 hour, a second dose of CINRYZE may be administered (1000 U for subjects ≥6 years of age or 500 U for subjects 2-5 years of age).

It is recommended that treatment of breakthrough attacks occurs at the investigational site whenever possible so that clinical assessments can be completed as specified. It is preferred that subjects receive CINRYZE within 4 hours but not more than 8 hours after the onset of breakthrough attack symptoms if treatment can occur at the investigational site.

Subjects (at least 12 years of age or their caregivers) who have completed the required self-administration training and deemed independent (per criteria specified in Section 5.3.1) may elect to self-administer CINRYZE for a breakthrough attack. Note: Subjects (or caregivers) who are participating in self-administration training and not yet qualified as independent cannot self-administer CINRYZE for a breakthrough attack; rather they must seek treatment at the investigational site. If a subject (or caregiver) who self-administers CINRYZE for treatment of a breakthrough attack does not respond adequately after instructed treatment (ie, 2 doses separated by 1 hour), they should notify the Investigator and seek medical attention or report to study site to seek further treatment and relief of symptoms.

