## 5.2. ANALYSIS POPULATIONS

Enrolled subjects are all subjects who signed signed informed consent and completed screening.

All treated subjects (ie, Intent-to-Treat Safety [ITT-S] Population: subjects who receive any amount of study drug) will be included in the safety analyses.

Full Analysis Set Population (defined as subjects who have at least one post baseline efficacy assessment) will be included in the efficacy analyses.

All subjects with evaluable PK/PD profiles (ie, PK/PD Population) will be included in PK/PD analyses as appropriate.

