# 5.9. IMMUNOGENICITY (C1-INH ANTIBODY) AND PHARMACOKINETIC CONCENTRATIONS AND PHARMACODYNAMICS LEVELS

The concentrations of C1-INH antigen (protein volume), functional C1-INH activity (potency), and complement C4 and C1q for individual subjects will be determined using fully validated bioanalytical methods, and will be listed and summarized using descriptive statistics at each time point. C1q concentrations will be assessed at baseline only (ie, pre-infusion, Dosing Visit 1).

The Antibody results will be listed and summarized using descriptive statistics at each nominal time point.

\\SW20RND01\VistaTempDir\Temp28232\Shire 0624 209 SAP v1 0.docx Document: PPD Version Number: Author:

Version Date: 21Jul2017

Template No: CS\_TP\_BS016 Revision 4

PROTOCOL: 0624-209 Page 26 of 35

1.0

21Jul2017

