#### 9.1.3. LIST OF PLANNED LISTINGS

Listing 16.2.1.1 Subject Disposition (All Enrolled Subjects)

Document: \\SW20RND01\\VistaTempDir\Temp28232\\Shire\_0624\_209\_SAP\_v1 0.docx

Author: PPD Version Number: 1.0
Version Date: 21Jul2017

Template No: CS TP BS016 Revision 4 Reference: CS WI BS005

Shire
PROTOCOL: 0624-209
Page 31 of 35

Listing 16.2.1.2 Subjects Who Terminated from the Study (All Enrolled Subjects)

Listing 16.2.2.1 Deviations from Inclusion/Exclusion Criteria (All Enrolled Subjects)

Listing 16.2.2.2 Protocol Deviations (All Enrolled Subjects)

Listing 16.2.4.1 Subject Demographic and Baseline Characteristics (Intent-to-Treat Safety Analysis Set)

Listing 16.2.4.3.1 Hereditary Angioedema (HAE) History (Intent-to-Treat Safety Analysis Set)

Listing 16.2.4.3.2 Hereditary Angioedema (HAE) History Detail (Intent-to-Treat Safety Analysis Set)

Listing 16.2.4.3.3 Medical History (Intent-to-Treat Safety Analysis Set)

Listing 16.2.4.4.1 Prior and Concomitant Medications (Intent-to-Treat Safety Analysis Set)

Listing 16.2.4.4.2 Concomitant Medical/Surgical Procedures (Intent-to-Treat Safety Analysis Set)

Listing 16.2.5.2.1 Study Drug Administration (Intent-to-Treat Safety Analysis Set)

Listing 16.2.5.2.2 Study Drug Exposure (Intent-to-Treat Safety Analysis Set)

Listing 16.2.5.3 C1-INH Antigen, Functional C1-INH activity, Complement C4 and C1q (Intent-to-Treat Safety Analysis Set)

Listing 16.2.5.4 Antibody Results (Intent-to-Treat Safety Analysis Set)

Listing 16.2.6.1 Subject Data of Angioedema Attack (Intent-to-Treat Safety Analysis Set)

Listing 16.2.6.2 Subject Data of Breakthrough Attack (Intent-to-Treat Safety Analysis Set)

Listing 16.2.6.3 Investigator Assessment of Breakthrough Attack (Intent-to-Treat Safety Analysis Set)

Listing 16.2.6.4 Self-administration Survey (Intent-to-Treat Safety Analysis Set)

Listing 16.2.6.5 Treatment Compliance (Intent-to-Treat Safety Analysis Set)

Listing 16.2.7.1 Adverse Events (Intent-to-Treat Safety Analysis Set)

Listing 16.2.7.2 Serious Adverse Events (Intent-to-Treat Safety Analysis Set)

Listing 16.2.8.1.2 Clinical Laboratory Test Results (Intent-to-Treat Safety Analysis Set)

Listing 16.2.8.1.3 Subjects with Potentially Clinically Important Laboratory Test Results (Intent-to-Treat Safety Analysis Set)

Listing 16.2.8.2.1 Vital Signs (Intent-to-Treat Safety Analysis Set)

Listing 16.2.8.2.2 Subjects with Potentially Clinically Important Vital Signs (Intent-to-Treat Safety Analysis Set)

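### The SAP's only PK/PD concentration table uses ITT-S instead of the assigned PK/PD Population, and no rule covers scheduled samples taken after supplemental C1 INH

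*SAP*

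**What the plan says.** **Population.** SAP 5.2, in the same words as protocol 7.2, states: "All subjects with evaluable PK/PD profiles (ie, PK/PD Population) will be included in PK/PD analyses as appropriate". Neither document defines 'evaluable'. SAP 5.2 gives ITT-S a different purpose: "subjects who receive any amount of study drug) will be included in the safety analyses".

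**Planned outputs.** SAP 9.1.1 lists "Table 14.2.3.1 C1-INH Antigen, Functional C1-INH activity, Complement C4 and C1q (Intent-to-Treat Safety Analysis Set", and SAP 9.1.3 lists "Listing 16.2.5.3 C1-INH Antigen, Functional C1-INH activity, Complement C4 and C1q (Intent-to-Treat Safety Analysis Set". No table, figure or listing in SAP Appendix I names the PK/PD Population. SAP 6.2 declares one departure from the protocol (clinical relief), and it is not this one.

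**Summary rule.** Under SAP 5.9 the concentrations "will be listed and summarized using descriptive statistics at each time point". SAP 5.1 keeps unscheduled-visit data out of the analyses and shows them in listings only.

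**Supplemental dosing.** Protocol 6.12.1: "If a breakthrough angioedema attack occurs during the 12-week treatment period through 1-week post-treatment, a supplemental dose of CINRYZE may be administered", with a second dose possible if the response is inadequate. Subjects so treated are told that "they should continue their protocol-defined treatment schedule without alteration regardless of when the supplemental dose is administered". Another C1 INH product may be given at the site if CINRYZE fails.

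**Sampling.** Protocol Schedule 4 takes serial samples after Doses 1 and 24, the last at "96 hours after start of infusion", and pre-dose samples at Visits 1, 3, 5 and 24.

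**The concern.** There are two separate gaps.

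The first is a contradiction about the analysis set. A population is defined for PK/PD and then never used, while the PK/PD table is put on the safety set without a declared change.

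The second is a missing sample-level rule. Supplemental C1 INH raises the same antigen and activity levels that the scheduled samples are meant to measure. It may be given at any time in the sampling windows, and the twice-weekly schedule carries on around it. SAP 5.1 takes care of samples drawn at the attack itself, because protocol 6.8 classes those as unscheduled. It does not touch later scheduled samples that still carry the supplemental dose.

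PK/PD in Japanese subjects is a stated objective, and protocol 7.3 allows the results to be superimposed on overseas data. SAP Appendix I lists no PK parameter table, so within the SAP the nominal-time summaries are the whole PK/PD result. The plan requires only 6 completers, so one affected profile can visibly raise a mean.

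**Working it through.** The plan states no size for the PK/PD Population and no PK precision target, so there is no figure to reproduce. The check has a textual part and an illustration of scale.

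**1. Labels side by side**

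| Place | Set for PK/PD |
|---|---|
| Protocol 7.2 | PK/PD Population |
| SAP 5.2 | PK/PD Population |
| SAP 9.1.1, Table 14.2.3.1 | ITT-S |
| SAP 9.1.3, Listing 16.2.5.3 | ITT-S |
| SAP 6.2 | no change declared |

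**2. Overlap in time.** Supplemental CINRYZE is allowed from the treatment period through 1 week after it. This covers the profile after Dose 1, the days before the Visit 3, 5 and 24 pre-dose samples, and the full 96 h after Dose 24.

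**3. Size of the shift.** Inputs from protocol 1.1.2 (overseas): functional activity rises from 0.31 to 0.68 U/mL after 1000 U, with a half-life of about 60 h. Assumptions: one-compartment decay, additive doses, n = 6.

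- Rise from one dose: 0.68 − 0.31 = 0.37 U/mL.
- Remainder of Dose 1 at 72 h: 0.37 × 0.5^(72/60) = 0.161 U/mL. Uncorrected level: 0.31 + 0.161 = 0.471 U/mL.
- Supplemental dose near its peak in one subject: 0.37/6 = 0.062 U/mL. As a share: 0.062/0.161 = 38% corrected, 0.062/0.471 = 13% uncorrected.
- Supplemental dose 24 h old: 0.37 × 0.5^(24/60)/6 = 0.280/6 = 0.047 U/mL, which is 29% corrected and 10% uncorrected.
- Visit 24 at steady state, taking an 84 h interval: accumulation 1/(1 − 0.5^(84/60)) = 1.61, so the 72 h rise is 0.161 × 1.61 = 0.259 U/mL. One peak-timed dose then gives 0.062/0.259 = 24% corrected and 0.062/0.569 = 11% uncorrected.
- With n = 8, the peak-timed Dose 1 shift is 0.37/8 = 0.046 U/mL (29% and 10%).

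**4. How likely.** P(at least 1 of 6 has a C1 INH-treated attack) = 1 − exp(−6 × 8 × r × f). The 8 days are two 96 h windows, r is attacks per day and f the share treated with C1 INH. The documents give no f, so 25% to 100% is assumed.

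| Attack rate | f = 25% | f = 100% |
|---|---|---|
| 0.25 per month (assumed) | 9% | 33% |
| 1 per month (entry minimum, protocol 4.1) | 33% | 79% |
| 6.3 per 12 weeks (overseas on-treatment mean, protocol 1.1.2) | 59% | 97% |

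**5. Length of a look-back for pre-dose samples.** The table gives the residual of one dose, its effect on a mean of 6, and the chance that a given subject loses the Visit 24 pre-dose value if every attack were treated, 1 − exp(−days × r).

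| Look-back | Residual (U/mL) | Shift in mean | Loss at 1/month | Loss at 6.3/12 weeks |
|---|---|---|---|---|
| 120 h (2 half-lives) | 0.37/4 = 0.093 | 0.015 | 15% | 31% |
| 180 h (3 half-lives) | 0.37/8 = 0.046 | 0.008 | 22% | 43% |
| 300 h (5 half-lives) | 0.37/32 = 0.012 | 0.002 | 34% | 61% |

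**The case against.** The case on the other side has several good parts.

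- **The label does not cause the mixing.** A reader might infer that running the table on ITT-S is what lets affected samples in. The documents do not support that. The PK/PD Population is a set of subjects, used as appropriate, and 'evaluable' is undefined. If it means only that enough samples were collected, a subject given supplemental C1 INH stays in and the means do not change. With about 6 subjects the two sets may be identical. This stands: the label and the missing sample rule are two gaps, and changing the label alone would not close the second.
- **Nothing shows that it happened.** A reader might take it as fact that raised concentrations are in the means. The documents do not report whether any supplemental dose fell in a sampling window. This stands.
- **Some handling exists.** Samples drawn at the attack stay out of the summaries. Sample times are recorded, and the study drug listing (16.2.5.2.1) would let a reader trace an affected CINRYZE profile. That helps a reader of the listings but does not correct the table.
- **The largest percentages are a special case.** One peak-timed dose gives 38%, and two give 0.54/6 = 0.09 U/mL, or 56%, both of the baseline-corrected Dose 1 value at 72 h. Protocol 7.5 plans summaries with and without baseline correction, but SAP 5.9 mentions none. Uncorrected, the shares are 13% and 19%. The attack rates are also borrowed: one is a pre-enrolment entry minimum, the other comes from an overseas study whose placebo rate was 12.8 per 12 weeks. The percentages therefore show scale only.

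None of this explains a population that is defined and never used, or supplies a rule for affected scheduled samples.

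**Conclusion.** The point holds in two parts. First, the analysis set of Table 14.2.3.1 and Listing 16.2.5.3 contradicts SAP 5.2 and protocol 7.2, and the change is not declared. This is a matter of text and needs no assumption. Second, 'evaluable' is undefined and SAP 5.9 has no rule for scheduled samples taken after supplemental C1 INH. Following the plan as written would therefore average such values in if they occur, biasing the means upward.

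The plausible size, for one affected subject of 6 with one supplemental dose, is about 0.05-0.06 U/mL on the 72 h Dose 1 mean: 29-38% baseline-corrected, about 10-13% uncorrected. The relative shift is smaller at steady state. The chance that it arises in the two windows is anywhere from about 9% to 97%. These figures rest on overseas means, additivity, one-compartment decay, Poisson attacks and an assumed treated share. They are not trial results. The gap should be closed, because it touches a stated objective and is cheap to close. It does not show that the PK/PD results are wrong.

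**What to change.** 1. In SAP 5.2, define 'evaluable', at subject level and for each profile.
2. Run Table 14.2.3.1 on the PK/PD Population, in line with SAP 5.2 and protocol 7.2.
3. In SAP 5.9, state that scheduled concentrations taken after supplemental CINRYZE, other C1 INH or a blood product are flagged and left out of the main nominal-time means. This applies to the rest of that profile, and to pre-dose samples within a stated look-back.
4. Justify the look-back from the half-life and keep it shorter than 300 h; 2-3 half-lives (120-180 h) is one example. At 300 h the residual is negligible, but 34-61% of Visit 24 pre-dose values could be lost if every attack were treated.
5. Flag the excluded values in Listing 16.2.5.3, so that every value remains visible.
6. Keep the all-subject table as the sensitivity version.

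The cost is SAP wording, one flag variable and one extra table. CINRYZE infusion times (protocol 5.3) and sample times (protocol 6.8) are already recorded. For other attack medications protocol 6.5.2 names only start and stop dates, so for non-CINRYZE products the flag may have to be by day. Some time points will have fewer values, which the sensitivity table shows.

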#### 9.1.2. LIST OF PLANNED FIGURES

Figure 14.2.2.1.1.1 Kaplan Meier Plot - Time from Cinryze to Initial Improvement (Full Analysis Set)

Figure 14.2.2.1.1.2 Kaplan Meier Plot - Time from Cinryze to Complete Resolution (Full Analysis Set)

#### 9.1.3. LIST OF PLANNED LISTINGS

Listing 16.2.1.1 Subject Disposition (All Enrolled Subjects)

Document: \\SW20RND01\\VistaTempDir\Temp28232\\Shire\_0624\_209\_SAP\_v1 0.docx

Author: PPD Version Number: 1.0
Version Date: 21Jul2017

Template No: CS TP BS016 Revision 4 Reference: CS WI BS005

Shire
PROTOCOL: 0624-209
Page 31 of 35

Listing 16.2.1.2 Subjects Who Terminated from the Study (All Enrolled Subjects)

Listing 16.2.2.1 Deviations from Inclusion/Exclusion Criteria (All Enrolled Subjects)

Listing 16.2.2.2 Protocol Deviations (All Enrolled Subjects)

Listing 16.2.4.1 Subject Demographic and Baseline Characteristics (Intent-to-Treat Safety Analysis Set)

Listing 16.2.4.3.1 Hereditary Angioedema (HAE) History (Intent-to-Treat Safety Analysis Set)

Listing 16.2.4.3.2 Hereditary Angioedema (HAE) History Detail (Intent-to-Treat Safety Analysis Set)

Listing 16.2.4.3.3 Medical History (Intent-to-Treat Safety Analysis Set)

Listing 16.2.4.4.1 Prior and Concomitant Medications (Intent-to-Treat Safety Analysis Set)

Listing 16.2.4.4.2 Concomitant Medical/Surgical Procedures (Intent-to-Treat Safety Analysis Set)

Listing 16.2.5.2.1 Study Drug Administration (Intent-to-Treat Safety Analysis Set)

Listing 16.2.5.2.2 Study Drug Exposure (Intent-to-Treat Safety Analysis Set)

Listing 16.2.5.3 C1-INH Antigen, Functional C1-INH activity, Complement C4 and C1q (Intent-to-Treat Safety Analysis Set)

Listing 16.2.5.4 Antibody Results (Intent-to-Treat Safety Analysis Set)

Listing 16.2.6.1 Subject Data of Angioedema Attack (Intent-to-Treat Safety Analysis Set)

Listing 16.2.6.2 Subject Data of Breakthrough Attack (Intent-to-Treat Safety Analysis Set)

Listing 16.2.6.3 Investigator Assessment of Breakthrough Attack (Intent-to-Treat Safety Analysis Set)

Listing 16.2.6.4 Self-administration Survey (Intent-to-Treat Safety Analysis Set)

Listing 16.2.6.5 Treatment Compliance (Intent-to-Treat Safety Analysis Set)

Listing 16.2.7.1 Adverse Events (Intent-to-Treat Safety Analysis Set)

Listing 16.2.7.2 Serious Adverse Events (Intent-to-Treat Safety Analysis Set)

Listing 16.2.8.1.2 Clinical Laboratory Test Results (Intent-to-Treat Safety Analysis Set)

Listing 16.2.8.1.3 Subjects with Potentially Clinically Important Laboratory Test Results (Intent-to-Treat Safety Analysis Set)

Listing 16.2.8.2.1 Vital Signs (Intent-to-Treat Safety Analysis Set)

Listing 16.2.8.2.2 Subjects with Potentially Clinically Important Vital Signs (Intent-to-Treat Safety Analysis Set)

Listing 16.2.8.3.1 12-lead ECG Results and Interpretation (Intent-to-Treat Safety Analysis Set)

